2.1.4 Safety endpoints

The safety analysis will be based on the reported AEs and other safety information, such as clinical laboratory data, vital signs, ECG and ECOG performance status ([Section 1.4](#)).

Observation period

The observation period will be divided into 3 periods: pre-treatment, on-treatment, and post-treatment including the extended safety follow-up period.

- The **pre-treatment period** is defined as the time from when the patient gave informed consent and the start of study treatment administration.
- The **on-treatment period** is defined as the time from the first dose of study treatment up to 30 days after the last dose of study treatment.
- The **post-treatment period** is defined as the time starting the day after the end of the on-treatment period up to the end of the study (as defined in the protocol).
 - The **extended safety follow-up period** is defined as the time period from 31 days after the last dose of study treatments to 90 days after the last dose of study treatments.

2.1.4.1 Adverse events variables

Adverse events occurring from signature of informed consent form up to 30 days after the last study treatment administration will be recorded in the eCRF. In addition, all study treatment related AEs and serious AEs (SAEs) ongoing at time of study treatment discontinuation will be followed during the follow-up period until resolution or stabilization.

All AEs (including SAEs) will be coded to a lower-level term (LLT), preferred term (PT), high-level term (HLT), high-level group term (HLGT), and associated primary system organ class (SOC) using the version of MedDRA in effect at Sanofi at the time of database lock.

The severity of AEs will be assessed according to NCI-CTCAE Version 4.03.

The following AEs will be described:

- **Pre-treatment AEs:** defined as any AE reported during the pre-treatment period.
- **Treatment-emergent AEs (TEAEs):** defined as any AE developed, worsened (according to the Investigator's opinion), or became serious during the on-treatment period.
- **Post-treatment AEs:** defined as any AE developed, worsened (according to the Investigator's opinion), or became serious during the post-treatment period.
 - **Extended safety follow-up period AEs:** defined as any AE developed, worsened (according to the Investigator's opinion), or became serious during the extended safety follow-up period.

In addition, deaths ([Section 2.1.4.2](#)), SAEs, AEs leading to withdrawal, and other significant AEs will be analyzed. Other significant events will include:

Adverse events of special interest (AESIs):

- Grade ≥ 2 acute infusion reactions (IRs).
- Grade ≥ 3 immune-related TEAEs.
- Any grade of treatment emergent immune-related AEs (irAE) in a patient previously treated with a Pi3K inhibitor.
- DLTs (for Phase 1 part only).
- Symptomatic overdose with IMP/NIMP.
- Pregnancy occurring in a female patient or in a female partner of a male patient.

Infusion reactions

Infusion reactions typically occur within 24 hours from the start of each cemiplimab/isatuximab infusion. As described above, Grade ≥ 2 IRs are AESIs.

Whenever possible, a diagnosis of the IR (eg, Cytokine release syndrome, infusion related reaction, anaphylactic reaction, or any other terms chosen by the investigator) will be reported by the investigator on a specific AE page instead of individual symptoms. Each IR diagnosis will be reported as related to isatuximab, cemiplimab or NIMP (eg, premedication). In addition, symptoms of the IRs will be reported on a separate eCRF form.

The primary analysis of IR will include all events regardless of the relationship to isatuximab, cemiplimab or NIMP.

One type of IR analysis will be performed based on the investigator's reporting of IR (diagnosis or symptoms).

Another type of IR analysis will include TEAEs (one table including related TEAEs, one table including all TEAEs regardless of relationship) occurring within 24 hours from the start of each infusion of isatuximab and/or cemiplimab (ie, TEAEs with onset on the same calendar day of the cemiplimab/isatuximab infusion or on the following day).

A similar type of analysis including TEAEs occurring within 24 hours from the start of each infusion and within the within 24 hours in the "Hypersensitivity and CRS" CMQ will also be performed.

Moreover, all the TEAEs (not only limited to those occurring within 24h of each infusion) from the above listed CMQ will also be analyzed.

If relevant (see [Section 2.4.5.2](#)), additional analyses of IR will be performed separately for IRs related to isatuximab or to cemiplimab.

IRs related to NIMP (if any) will be reported in a listing.

Immune-related AEs

Immune-related AEs are typically associated with immune checkpoint inhibitors (2). The symptoms of irAEs may be subtle (Amended Protocol Version 3.0, Section 6.5.4) and may include, but not limited to, colitis, endocrine AE, pneumonitis, renal AE, dermatologic AE, hepatitis, ophthalmologic AE (Uveitis), nausea and vomiting. Because irAEs could occur long after exposure with immune checkpoint inhibitors, the irAE analysis will not be limited to the on-treatment period, but also include the extended safety follow up period.

Different types of irAE analysis will be performed.

- Grade ≥ 3 irAEs reported as AESIs: include all AESIs and exclude IRs, pregnancy, symptomatic overdose and DLT (if any).
- TEAEs plus extended safety follow-up AEs (related to cemiplimab; regardless of relationship).
- TEAEs plus extended safety follow-up AEs from sponsor selected grouping of PTs (related to cemiplimab; regardless of relationship).

Respiratory AEs

Analysis of respiratory TEAEs will focus particularly on the following groupings:

- Lower Respiratory adverse events, selected using CMQ ‘Lower respiratory events’.
- Respiratory infections, selected using CMQ ‘Respiratory infections’.

In addition, respiratory adverse events with late onset (ie, occurring, worsening or becoming serious more than 30 days after last dose) will be analyzed as part of the post-TEAEs analysis.

Cardiac AEs

Analysis of cardiac adverse events will focus particularly on SMQ “Cardiac failure” (narrow).

Neutropenia and neutropenic complications

Neutropenia, febrile neutropenia and neutropenic infections will be analyzed using the following data source:

- Neutropenia based on laboratory results.
- Febrile neutropenia selected using CMQ ‘Febrile neutropenia’.
- Neutropenic infections: defined as NCI-CTCAE Grade ≥ 2 infections from SOC Infections and Infestations’ (selected using CMQ ‘GLB_SOC infections and infestations’) concomitant with NCI-CTCAE Grade 3-4 neutropenia from laboratory results. Infection and Grade 3-4 neutropenia will be considered as concomitant if one of the following condition is met:
 - Neutrophils count value measured the day of the start of the AE infection,
 - The last neutrophils count value measured before the start date of the AE infection is within 7 days before the start of the AE infection,
 - The first neutrophils count value measured after the start date of the AE infection is within 2 days after the start of the AE infection.

Thrombocytopenia and hemorrhages

- Thrombocytopenia will be analyzed based on laboratory results.
- Hemorrhages will be selected using the TEAEs from the SMQ ‘Haemorrhage terms (excl laboratory terms)’.
- Moreover, severe thrombocytopenia (ie, \geq Grade 4) with concomitant hemorrhage will be displayed if relevant. The first hemorrhages event occurring within 8 days after any occurrence of the thrombocytopenia (Lab) will be used for this analysis.

Hemolytic disorders

Hemolytic disorders will be selected using the TEAEs from the CMQ ‘Haemolytic disorders Broad’.

Tumor lysis syndrome

Tumor lysis syndrome will be identified using CMQ ‘Tumour lysis syndrome’.

Second primary malignancies

Second primary malignancies will be selected using CMQ ‘Second primary malignancies’

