10.5 ADVERSE EVENT OF SPECIAL INTEREST

An AESI is an AE (serious or nonserious) of scientific and medical concern specific to the Sponsor's product or program, for which ongoing monitoring and immediate notification by the Investigator to the Sponsor is required. Such events may require further investigation in order to characterize and understand them. Adverse events of special interest may be added, modified or removed during a study by protocol amendment.

The following conditions are considered AESIs and as such, the Investigators will be required to report them to the Sponsor within 24 hours of the Investigator becoming aware of the event:

- **Grade ≥ 2 acute infusion associated reactions (IARs;** [Section 6.5.4](#) for manifestation/symptoms typical of an IAR). An IAR occurs typically within 24 hours from the start of the infusion.
- **Grade ≥ 3 immune-related TEAEs.**
- Any grade of **immune-related TEAEs** in a patient previously treated with a PI 3-K inhibitor.
- **DLTs** (as defined in [Section 9.1.1](#)) are considered as AESIs, and as such, the Investigators will be required to report them to the Sponsor within 24 hours of the Investigator becoming aware of the event. The Investigator will attach the DLT-specific CRF page to the DLT/AESI form.
- **Pregnancy** of a female subject entered in a study as well as pregnancy occurring in a female partner of a male subject entered in a study with IMP/NIMP.

- Pregnancy occurring in a female patient entered in the clinical trial or in a female partner of a male patient entered in the clinical trial. It will be qualified as an SAE only if it fulfills one of the seriousness criteria (see [Section 10.4](#)),
- In the event of pregnancy in a female participant, treatment with the IMP should be discontinued,
- Follow-up of the pregnancy in a female participant or in a female partner of a male participant is mandatory until the outcome has been determined.
- **Symptomatic overdose** (serious or nonserious) with IMP/NIMP (see [Section 10.4.2](#)):
 - An overdose (accidental or intentional) with the isatuximab or cemiplimab is defined as increase of at least 30% of the intended administered dose at each infusion expressed in unit per body weight) to be administered in the specified duration or if the dose is administered in less than half the recommended duration of administration,

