13.4.5.2 Analyses of adverse events

The observation period will be divided into 3 segments: screening, TEAE and post-treatment:

- The screening period is defined as the time informed consent is signed until the first dose of study treatments administration.
- The TEAE period is defined as the time from the first dose of study treatments up to 30 days after last dose of study treatments.
- The post-treatment period is defined as the time starting 31 days after the last dose of study treatments to study closure or death, whichever comes first.

Pre-treatment AEs are defined as any AE during the screening period.

Treatment-emergent AEs are defined as AEs that develop, worsen (according to the Investigator opinion), or become serious during the TEAE period.

Post-treatment AEs are defined as AEs that are reported during the post-treatment period.

The grade will be taken into account in the summary. For patients with multiple occurrences of the same PT, the maximum grade will be used.

The primary focus of AE reporting will be on TEAEs. Pre-treatment and post-treatment AEs will be described separately.

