 - Duration (in days).
- Number of patients with symptoms of IRs (as reported by investigator).
- Number (%) of patients experiencing TEAEs (related and regardless of causal relationship) within 24 hours from the start of each infusion.
- Similar tables including all TEAEs within 24 hours from the start of each infusion from the selected list of CMQ (see [Section 2.1.4.1](#)).
- Number (%) of patients experiencing TEAEs (related and regardless of causality), (not only limited to those occurring within 24h of each infusion) from the selected list of CMQ (see [Section 2.1.4.1](#)).

If the IR rate is much higher ($\geq 20\%$) in combination arms than in the control arm, additional analyses of IR might be performed separately for isatuximab and cemiplimab.

A listing of IRs that are related to NIMP will be provided.

Immune related AEs:

Because irAEs could occur long after exposure with immune checkpoint inhibitors, the irAE analysis will include both on-treatment period and extended safety follow up period. As noted in [Table 7](#), the analysis will include:

- Number (%) of patients experiencing irAEs reported as AESI by investigator: include all AESI and exclude IRs, pregnancy, symptomatic overdose and DLT (if any).
- Number (%) of patients experiencing AEs from selected grouping of PTs occurring during the treatment emergent and extended safety follow up periods (one analysis for events related to cemiplimab; another analysis for regardless of relationship).
- Number (%) of patients experiencing AEs occurring during the treatment emergent and extended safety follow up periods (one analysis for events related to cemiplimab; another analysis for events regardless of relationship).

Respiratory TEAEs:

Respiratory TEAEs will be analyzed using selection defined in [Section 2.1.4.1](#) and will be presented by PT.

Cardiac TEAEs

Cardiac TEAEs will be analyzed using selection defined in [Section 2.1.4.1](#) and will be presented by PT, sorted by decreasing incidence.

Analysis of pre-treatment and post-treatment adverse events

The following frequency distributions of AEs (incidence tables) will be provided for the safety population, for all grades combined and Grade ≥ 3 :

- All pre-treatment AEs by primary SOC and PT, showing the number (%) of patients with at least 1 pre-treatment AE, sorted by the internationally agreed SOC order and decreasing incidence of PTs within each SOC.

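### The Grade 3 or higher immune-related AESI is defined as treatment-emergent, so the AESI-based irAE table cannot reliably cover days 31-90, which the SAP says irAE analysis includes

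*SAP*

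**What the plan says.** **Window for irAE analysis.** SAP 2.1.4.1 gives possible late onset after checkpoint inhibition as its reason and states that "the irAE analysis will not be limited to the on-treatment period, but also include the extended safety follow up period". SAP 2.4.5.2 repeats this ("the irAE analysis will include both on-treatment period and extended safety follow up period") and then lists the analyses concerned. The first of them is the number of patients with "irAEs reported as AESI by investigator".

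**Periods.** The SAP on-treatment period, which determines what counts as a TEAE, is the "time from the first dose of study treatment up to 30 days after the last dose of study treatment" (SAP 2.1.4). The protocol's TEAE period is the same (Protocol 13.4.5.2: "time from the first dose of study treatments up to 30 days after last dose of study treatments"). The extended safety follow-up period runs from "31 days after the last dose of study treatments to 90 days after the last dose of study treatments" (SAP 2.1.4).

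**AESI definition.** Protocol 10.5 lists Grade 3 or higher "immune-related TEAEs" as AESIs, to be reported within 24 hours. It adds any-grade immune-related TEAEs in patients previously given a PI3K inhibitor. SAP 2.1.4.1 carries the same two items, both limited to treatment-emergent events. Protocol 6.5.4 makes any-grade irAEs in the PI3K group AESIs and sets no treatment-emergent limit.

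**Collection after day 30.** Protocol 9.1.2 and 12.4.4.1 keep collecting new treatment-related AEs, serious or not, including at the 60- and 90-day visits.

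**The concern.** The AESI-based table takes its content from a definition that stops at day 30, while the section that plans it promises day 90. This table is also the one that draws on the investigator's own decision to report an event as an immune-related AESI. The other two irAE analyses use either all AEs or a sponsor-selected list of preferred terms. Attribution to cemiplimab, which those two also use, is a causality judgement and not an immune-mediated diagnosis.

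Safety of the combination is a primary objective (Protocol 5.1), and the control arm is there partly to show what risk cemiplimab adds (Protocol 4.3.3). If immune events can appear late, as the SAP says, a day-30 cut in this table would fall mainly on the cemiplimab arms. An investigator-flagged Grade 3 or higher irAE rate read as running to day 90 could then understate the late part. The definition also controls the 24-hour AESI clock, so it affects how quickly the sponsor hears of some late events.

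**Working it through.** No sample size, power or alpha figure enters this point. The check sets the definitions side by side.

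**Step 1: the two windows.** Eligibility as a TEAE, and so as a general immune-related AESI, runs from first dose to last dose + 30 days. The irAE window runs from first dose to last dose + 90 days. The difference is 90 − 30 = 60 days, namely days 31 to 90.

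**Step 2: what happens to a new Grade 3 or higher irAE that first arises on days 31-90.**

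| Question | Treatment-related and serious | Treatment-related and non-serious |
|---|---|---|
| Collected? | Yes (Protocol 9.1.2, 12.4.4.1) | Yes (same sections) |
| Meets the general AESI definition? | No (Protocol 10.5, SAP 2.1.4.1) | No |
| 24-hour entry? | Yes, as an SAE (Protocol 10.4.2) | Not under the 10.5 wording |
| In the AESI-based irAE table? | Only if the site flags it anyway | Only if the site flags it anyway |
| In the all-AE irAE analysis to day 90? | Yes | Yes |
| In the sponsor-selected PT analysis to day 90? | Yes, if the PT is on the list | Yes, if the PT is on the list |

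**Step 3: why the AESI row is not a flat no.** SAP 2.1.4.1 and 2.4.5.2 fill the table with all AESIs, less infusion reactions, pregnancy, symptomatic overdose and DLTs. Neither section applies a date filter. A late event that a site reports as an AESI would be counted, and the same event at a site that follows 10.5 literally would not.

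**Step 4: the prior PI3K-inhibitor item.** Under Protocol 6.5.4, an irAE of any grade on day 45, for example, is an AESI in these patients. Under Protocol 10.5 and SAP 2.1.4.1 it is not, because it is not treatment-emergent. If it is non-serious, whether the 24-hour clock applies depends on which section the site follows.

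**Step 5: count of analyses affected.** Of the three planned irAE analyses, one rests on the AESI flag. The other two explicitly add extended safety follow-up AEs. SAP Table 7 presents them by arm, with a Grade 3 or higher column.

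**The case against.** The strongest reply is that late irAEs are already analysed. Two of the three irAE analyses reach day 90, each run both as related to cemiplimab and regardless of relationship. Post-treatment AEs and SAEs are tabulated separately as well. This stands. A reader might infer that the irAE analysis as a whole stops at day 30, and the documents do not support that.

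Nor do they support reading the AESI-based table as necessarily empty after day 30. It has no date filter, and Protocol 10.4.3 foresees AESIs coming to light even after the end of study. This too stands, but it does not cure the problem: the content of the table then depends on site interpretation.

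A third tempting reading is that 24-hour reporting lapses altogether after day 30. It does not. Protocol 10.4.2 requires 24-hour entry for SAEs as well as AESIs and states no day-30 limit. What remains is the clock for non-serious events.

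It can also be said that the PI3K item is narrow, since prior idelalisib is an exclusion (Protocol 7.3), and that a new definition cannot re-create flags for follow-up already completed. The amendment history (Appendix K, amendment 05) shows that the primary and one-year analyses had been done by then. Both are fair. The same entry keeps benefiting patients on treatment and retains the 90-day safety period, so a corrected definition still has some prospective use.

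**Conclusion.** The mismatch is real and limited. For the general Grade 3 or higher item, both documents tie the AESI to treatment emergence, which ends at day 30. The SAP places the AESI-based table under a window that ends at day 90. One of three irAE analyses therefore cannot reliably cover its stated window, over a 60-day stretch. Expedited reporting is affected only for non-serious immune-related events after day 30. Separately, Protocol 6.5.4 conflicts with Protocol 10.5 and SAP 2.1.4.1 on the prior PI3K-inhibitor group.

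The conclusion assumes that sites apply the AESI definition as written, and it concerns events that first arise after day 30. An event that began on treatment and worsened later is arguably still a TEAE. The 60 days is the length of a window and not an effect on results. No late-irAE rate is given, so the number of events missed is unknown and could be zero.

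**What to change.** In Protocol 10.5 and SAP 2.1.4.1, define the Grade 3 or higher immune-related AESI by onset from first dose to 90 days after last dose, which matches the SAP's irAE window. This also settles the reporting clock for non-serious Grade 3 or higher irAEs after day 30. Reconcile Protocol 6.5.4 with Protocol 10.5 and SAP 2.1.4.1 so that the prior PI3K-inhibitor item has one window throughout.

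For data already collected, label the AESI-based table as treatment-emergent only, apply that limit so the label is true, and refer the reader to the other two irAE analyses for days 31-90.

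The cost is one definition in each document, one reconciliation and a table label. The downside is a few more 24-hour reports. The new related events are already being collected at the 60- and 90-day visits, so no extra assessment is needed.

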- Bone Marrow for disease assessment ^{ee}	X	to confirm CR and as clinically indicated						X (if clinically indicated)	X (if clinically indicated) ^{dd}		
- Bone disease assessment (Skeletal survey or low-dose whole body CT) ^{ff}	X					X (if clinically indicated)		X (if clinically indicated)	X (if clinically indicated) ^{dd}		
- Plasmacytoma assessment (PET/CT/MRI) ^{gg}	X					X (if clinically indicated)		X (if clinically indicated)	X (if clinically indicated) ^{dd}		
Isatuximab Administration ^{hh}		X	X	X	X	X	X				

Evaluation ^a	Screening/ Baseline	Cycle 1 ^b				Subsequent Cycles ^b		End of Treatment (EOT)	Post treatment Follow-up Period ⁱⁱ		
	D-21 to D1	D1	D8	D15	D22	D1	D15	30 days after last IMP admin	At 60 days after last IMP admin	At 90 days after last IMP admin	Beyond 90 days after last IMP admin
Cemiplimab Administration		X		X		X	X				
AE/SAE Assessment ⁱⁱ	X	Continuously throughout study period						X (ongoing related AE, ongoing SAE, new related AE/SAEs)			
Prior/Concomitant Medication	X (within 21 days prior to first dose)	Continuously throughout study period						X (related to AE/SAEs)			
- New anticancer therapy								X	X		

- a **Evaluation:** Assessments to be performed prior to study treatment and prior to premedication administration unless otherwise indicated. Informed consent should be signed before any study specific procedures. In Phase 2 part, **randomization** to take place once the consented patient has completed all the necessary screening procedures and is deemed eligible for study entry by the Investigator or designee. All eligible patients must be randomized using Interactive Response Technology (IRT). Every effort should be made to start treatment within 3 working days of randomization.
- b **Cycle:** A cycle is 28 days. The treatment window is ± 1 day for each of the weekly administrations ± 2 day for each of the Q2W administrations and ± 4 day for each of the Q4W administrations. A dose is deemed to have been delayed if the treatment is ≥ 2 days beyond the theoretical day of treatment for weekly dose, ≥ 3 days beyond the theoretical day of treatment for Q2W dose and ≥ 5 days beyond the theoretical day of treatment for Q4W dose. The reason for dose delay will be captured. Cycle 1 Day 1 refers to the day the patient receives the first study treatment administration.

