2.4 STATISTICAL METHODS

Unless otherwise specified, analyses will be descriptive and performed separately for Phase 1 and Phase 2 patients, based on the analysis population defined in [Section 2.3](#).

For Phase 1 part, when the number of treated patient is small (<5), baseline information together with listings on response and adverse events will be provided. Summary tables might be presented if deemed appropriate.

In Phase 2 summary tables (except for demographics and baseline characteristics), treatment arms will be presented as follows:

- Isatuximab 10 mg/kg QW/Q2W (Isa).
- Isatuximab 10 mg/kg QW/Q2W + cemiplimab 250 mg Q2W (Isa + CemQ2W).
- Isatuximab 10 mg/kg QW/Q2W + cemiplimab 250 mg Q4W (Isa + CemQ4W).

Parameters on demographics and baseline characteristics would be provided by treatment arms and overall.

Continuous data will be summarized using the number of available data, mean, standard deviation (SD), median, minimum, and maximum for each arm. Categorical and ordinal data will be summarized using the number and percentage of patients in each arm.

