SOC and PT	
 Primary SOC: internationally agreed order PT: decreasing order of frequency of Isa + CemQ2W arm 	
By treatment arms (and all patients if Phase 1): n (%) of patients with any event and n (%) of patients with event of Grade ≥3
	
 All TEAEs TEAEs occurring in ≥5% of the patients (in any group for Phase 2) Drug-related TEAEs Serious TEAEs Drug related serious TEAEs TEAEs leading to isatuximab discontinuation TEAEs leading to cemiplimab discontinuation TEAEs leading to dose interruption of isatuximab TEAEs leading to dose interruption of cemiplimab TEAEs leading to dose delay of isatuximab TEAEs leading to dose delay of cemiplimab TEAEs leading to dose reduction^a of isatuximab TEAEs leading to dose reduction^a of cemiplimab Pre-treatment AEs; Serious pre-treatment AEs Post-treatment AEs; Serious post-treatment AEs

MedDRA variables	Sorting	Layout	Events
SOC and PT	
 Primary SOC: internationally agreed order PT: decreasing order of frequency of Isa + CemQ2W arm 	
By treatment arms (and all patients if Phase 1): n (%) of patients with any event and n (%) of patients with event of Grade ≥ 3
	
IR analysis:
 
 IR diagnosis (as reported by investigator) Symptoms of IR (as reported by investigator) TEAEs (related; regardless of relationship) within 24 hours from the start of each infusion TEAEs (related; regardless of relationship) from the selected CMQ within 24 hours from the start of each infusion TEAEs (related; regardless of relationship) from the selected CMQ (not limited to those occurring within 24 hours from the start of each isatuximab infusion)
SOC and PT	
 Primary SOC: internationally agreed order PT: decreasing order of frequency of Isa + CemQ2W arm 	
By treatment arms (and all patients if Phase 1): n (%) of patients with any event and n (%) of patients with event of Grade ≥ 3
	
irAE analysis:
 
 irAE reported as AESI by investigator AEs as defined by irAE selected grouping of AEs occurring during the treatment emergent and extended safety follow up periods (related to cemiplimab; regardless of relationship) AEs occurring during the treatment emergent and extended safety follow up periods (related to cemiplimab; regardless of relationship)

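### The any-relationship irAE tables run to day 90 after the last dose, but new events judged unrelated are collected only to day 30, so their counts are not all-cause

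*SAP*

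**What the plan says.** **Analysis window.** SAP 2.1.4 sets the extended safety follow-up as the time "from 31 days after the last dose of study treatments to 90 days after the last dose of study treatments". SAP 2.1.4.1 gives the reason for using it: "Because irAEs could occur long after exposure with immune checkpoint inhibitors, the irAE analysis will not be limited to the on-treatment period".

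**Tables.** Two event sets are pooled over both periods: all AEs, and a list of preferred terms chosen by the sponsor. Each has a version limited to events related to cemiplimab and a version with no limit on relationship. The second set is written as "TEAEs plus extended safety follow-up AEs from sponsor selected grouping of PTs (related to cemiplimab; regardless of relationship". SAP 2.4.5.2 repeats the pairing ("another analysis for regardless of relationship"), and Table 7 lists "AEs occurring during the treatment emergent and extended safety follow up periods (related to cemiplimab; regardless of relationship".

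**Collection.** SAP 2.1.4.1 says that AEs from consent "up to 30 days after the last study treatment administration will be recorded in the eCRF", and that related AEs and SAEs still ongoing at discontinuation are followed. The same section defines extended-period AEs without any limit on relationship. For the time after treatment, the AE row of the protocol flowchart (1.1) reads "ongoing related AE, ongoing SAE, new related AE/SAEs". Protocol 9.1.2, 10.4.1 and 12.4.4.1 agree with it: every AE is recorded to day 30, and after that new AEs only if related to study treatment.

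**The concern.** The any-relationship tables cover a period for which any-relationship data are not collected. The investigator's causality judgement, which these versions are meant to set aside, decides after day 30 whether a new event exists in the database at all.

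This matters for two reasons. First, the gap lies in the very window that the SAP added because irAEs may appear late. Second, these are the irAE tables best suited to a comparison with control. Patients on isatuximab alone receive no cemiplimab, so a table of events related to cemiplimab says little about them. Yet protocol 4.3.3 gives the control arm the task of showing what risk cemiplimab adds. A reader of one pooled count would take it as all-cause to day 90.

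**Working it through.** The documents give no figure to reproduce, and no event rate can be computed. The check sets the scope of the tables against the scope of collection.

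| Time after last dose | Scope of the any-relationship irAE tables | New AEs collected |
|---|---|---|
| To day 30 | Any relationship | Any relationship (SAP 2.1.4.1; protocol 1.1 footnote ii, 9.1.2, 10.4.1) |
| Days 31 to 90 | Any relationship | Only if judged related to study treatment (protocol 1.1, 9.1.2, 12.4.4.1, 12.4.4.2) |

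**Step 1: length of the affected window.** 90 − 31 + 1 = 60 days.

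**Step 2: number of tables.** 2 event sets × 2 relationship versions = 4 pooled irAE tables, of which 2 are any-relationship.

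**Step 3: does another rule restore the missing events?**
- AESI reporting (protocol 10.5; SAP 2.1.4.1) covers treatment-emergent irAEs only, and that period ends at day 30.
- Follow-up of existing events (protocol 10.4.3) concerns the outcome of AEs already recorded. After a patient's end of study it adds only events attributed to the study drug.
- The day 60 and day 90 visits (protocol 12.4.4.1) collect new AEs, serious or not, only if related.

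No section collects new unrelated AEs in days 31 to 90.

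**Step 4: what the any-relationship tables will contain for days 31 to 90.** They will hold new AEs related to either drug, plus worsening of ongoing SAEs and ongoing related AEs. They are therefore not the same as the cemiplimab-related versions: events attributed only to isatuximab, and worsening of an ongoing unrelated SAE, can still enter.

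**Step 5: direction within an arm.** Each table counts patients with at least one event. Adding uncollected events could only leave that count unchanged or raise it. So, in every arm, pooled count ≤ all-cause count to day 90.

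**Step 6: between arms.** The number of missing events depends on how many late events occurred, how many were judged unrelated, and how many patients were more than 30 days past their last dose at the cutoff. None of these is given by arm. The text describes no masking of investigators to arm, so attribution could differ between arms, but nothing fixes the direction.

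**The case against.** **The label can be read as a selection rule.** Paired with the cemiplimab-related version, it may mean only that no causality filter is applied to the recorded AEs. On that reading the programming is correct. This stands: a reader might infer that the label is simply false, and the documents do not support that. It is incomplete, because a filter was already applied at collection and the tables do not say so.

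**The periods are already shown apart.** SAP 2.4.5.2 describes post-treatment AEs separately, and Table 7 lists all TEAEs as well as post-treatment AEs. This stands in part. Restricting the all-AE irAE table to day 30 would only duplicate the planned table of all TEAEs. But that does not cover the sponsor's list of preferred terms, and the post-treatment period runs to the end of the study rather than to day 90. None of these tables states the limit on collection.

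**Little is lost.** Events judged unrelated to both drugs are the ones least likely to be true irAEs. Late events attributed to either drug are collected, and deaths with cause are summarised under SAP 2.4.5.3. By default the "analyses will be descriptive and performed separately for Phase 1 and Phase 2 patients", and no decision rule uses these tables. All of this stands and limits the importance of the point. It does not make the pooled count all-cause.

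**Two stronger inferences fail.** A reader might divide the 60 days by the 90 days after the last dose and call the result the share affected. The tables run from the first dose, so that ratio does not measure impact. A reader might also infer that the comparison with control is biased in a known direction; Step 6 shows that this cannot be determined.

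**Conclusion.** The point holds in a limited form. Two of the four pooled irAE tables will present counts that are all-cause to day 30 but, for new events, restricted by investigator causality from day 31 to day 90. In every arm they are lower bounds for the all-cause count to day 90. Only patients more than 30 days past their last dose at the cutoff are affected. The number of missing events and any effect on the arm comparison are unknown.

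The conclusion assumes that sites follow the collection rules as written and do not enter new unrelated AEs after day 30. It concerns the accuracy of a descriptive safety display. It does not touch the ORR analysis or any stopping rule. It is worth correcting because the SAP followed to the letter would produce a misleading table, and the correction is cheap.

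**What to change.** Change the SAP only.

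1. **All-cause comparison with control.** For the sponsor's list of preferred terms, add an any-relationship table limited to the on-treatment period (to day 30). For the all-AE set, refer to the table of all TEAEs already in Table 7.
2. **Days 31 to 90.** Either show this period separately or keep the pooled tables. In both cases put the limit in the title or a footnote, for example: *for days 31–90 only new AEs judged related to isatuximab or cemiplimab, and worsening of ongoing SAEs and ongoing related AEs, were collected*.
3. **SAP 2.1.4.1.** State that new related AEs are collected after day 30, as in the protocol, and bring the definition of extended-period AEs into line with what is collected.

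The cemiplimab-related versions can stay pooled to day 90. The cost is some SAP wording, a footnote, one added table, and a further display if days 31 to 90 are shown separately. The presentation becomes slightly less simple. No protocol amendment, eCRF change or new data is needed.
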